## 5.0 Study Intervention/Investigational Agent

5.1 Patients who consent for this study will undergo a series of BUS and noninvasive fecal calprotectin tests over the course of their enrollment. There are no known adverse effects of BUS.

## 6.0 Procedures Involved

6.1 Experienced research coordinators will screen for potentially eligible infants daily. NICU staff may notify someone from the study team about potential subjects. Infants successfully enrolled in the study will be clearly identified by signage at the bedside and updated lists in the work room. All enrolled subjects will have a baseline fecal calprotectin level obtained at the time of enrollment or with next stool. If an enrolled infant develops concern for NEC (as determined clinically by treating neonatologist), a sealed envelope will be opened to reveal to which arm the infant is randomized: **(A) AXR only (standard of care)** or **(B) AXR and BUS (intervention)**.

*Intervention.* Infants randomized to the **AXR only arm** will obtain an AXR as per standard of care (see **Figure**). Repeat AXR, if any, will be left to the discretion of the treating neonatologist. In this arm, no BUS study will be performed *unless* the attending neonatologist decides it is clinically indicated. This situation is expected to be exceedingly rare, as BUS is not part of the standard of care for NEC evaluation. Infants randomized to the **AXR and BUS arm** will also get an AXR, with repeat AXR left to the discretion of the treating neonatologist. In addition to this standard of care, infants randomized to this arm will receive a BUS as the intervention. This BUS will be ordered at the same time as the initial AXR and will be performed within six hours of the order being placed. Since CMH has overnight and weekend sonographers, BUS can be done performed 24/7. An additional BUS and fecal calprotectin level will be performed once every 24-hours until clinical suspicion is no longer warranted. Enrolled patients who may undergo multiple “suspected NEC” encounters during the course of their admission will remain in the same arm throughout the study.

**Figure:** Flow diagram of study following randomization.

Management. All AXR and BUS exams will be interpreted by board-certified pediatric radiologists, and all imaging results will be available for clinicians to review as part of the subject's medical record. Fecal calprotectin levels will be documented in the patient's research data, but not included in the subject's medical record. All laboratory tests and treatment, including antibiotics or bowel rest, will be left to the discretion of the treating neonatologist. Participation in the study will end at the time of discharge or transfer.

BUS performance and interpretation. US performance and interpretation will be performed by a sonographer and radiologist, respectively, as per standard clinical work-flow. All BUS results will be available to the study team (i.e. no blinding). Variability in performance of US by sonographers will be minimized by pre-study training and quick reference cards in each US machine as detailed above. Likewise, variability in US interpretation will be minimized by the pre-study training as well as the use of a standardized template for reporting US results (see **Appendix**). All study US exams will be over-read by the study radiologists to ensure accurate interpretation. In cases of differences in their readings, final interpretation will be made by the study radiologists and these results will be communicated to the clinical team.

Fecal calprotectin measurement. Stool will be collected from a diaper following study enrollment regardless of rate of feeds. We will do an additional collection of stool after five weeks of life to get a baseline calprotectin level. "Baseline" is defined as an infant who is greater than or equal to five weeks of age and is tolerating full enteral feeds of at least 120 mL/kg/day. All stool samples will be collected by the NICU nurse or study staff. Stools can be stored for up to 72 hours if needed and then processed using the Fecal Calprotection High Range Quantitative Quantum Blue assay. All results will be recorded in Redcap. If a baby develops a concern for NEC, the next three stool samples at least a day apart will be collected for FC analyzation. An additional stool sample will also be collected at the resolution of NEC watch, which is defined by tolerance of  $\geq 120$ mL/kg/day of enteral feeds for at least two days. Infants who have repeated concern for NEC will again have the first three stool samples collected with each event, with another stool also collected at resolution of NEC. The stool samples will be kept suspended in a buffer in a test tube for the duration of the study in the event a sample needs to be retested.

6.2 Protected health information (PHI) to be collected for the purpose of this study alone will include: DOB, gender, race, MRN, account number, dates of abdominal radiographs, ultrasound examinations, lab and vital signs. All data will be collected and kept in a password protected database (REDcap) that only CMH study personnel will have access to. A master linking list between MRN and study-ID numbers will be kept separately in REDcap and will be destroyed upon completion of the study. The research record generated will consist of an excel spreadsheet from the data dictionary within REDcap. Security measures include: storage of the

data on a password protected computer in a restricted access departmental folder limited to only study personnel.

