## 1.0 Study Summary

Study Title	Pilot Randomized Control Trial of Necrotizing Enterocolitis Screening using Abdominal Radiograph versus Bowel Ultrasound plus Abdominal Radiograph in Premature Neonates
Study Design	Pilot Randomized Controlled Trial
Primary Objective	To establish the feasibility and pilot the design and delivery of a diagnostic randomized controlled trial (RCT) of BUS for NEC evaluation.
Secondary Objective(s)	
 
• Explore whether the addition of BUS to the NEC diagnostic and monitoring pathway will change:             
 
1. The rates of medical versus surgical management
 
2. The days between NEC diagnosis and surgical intervention for those that need it
 
3. The days NPO for those that get medical management
 
 
 
• Develop a predictive model for NEC diagnosis
 
• Develop a predictive model for medical versus surgical management
 
• Explore the usefulness of serial fecal calprotectin levels as a predictive biomarker for NEC
 

Research Intervention(s)/Investigational Agent(s)	N/A
IND/IDE #	n/a
Study Population	Premature NICU babies under 32 weeks gestational age
Sample Size	160 subjects enrolled
Study Duration for Individual Participants	From enrollment until discharge or transfer from CMH
Study Specific Abbreviations/Definitions	NEC – Necrotizing Enterocolitis BUS – bowel ultrasound AXR – abdominal radiographs FC – fecal calprotectin NICU – Neonatal Intensive Care Unit CMH – Children's Mercy Hospital MRN – medical record number OSH – outside hospital LAR – legally authorized representative P/A/C – permission/assent/consent

	RCT – randomized controlled trial NPO – nothing by mouth VLBW – very low birth weight
--	---

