## 2.0 Objectives

2.1 The overall primary objective is to establish the feasibility and pilot the design and delivery of a diagnostic randomized controlled trial (RCT) of BUS (bowel ultrasound) for NEC evaluation which will lead to a successful application for a larger, multi-center clinical trial in the future. This program of research is anticipated to have a significant positive impact in the timely and accurate diagnosis of NEC in preterm infants.

We plan to accomplish our overall objective for this project by pursuing the following specific aims:

1. Explore whether the addition of BUS to the NEC diagnostic and monitoring pathway will change:
  - (a) The rates of medical versus surgical management
  - (b) The days between NEC diagnosis and surgical intervention for those that need it
  - (c) The days NPO for those that get medical management
2. Develop a predictive model for NEC diagnosis
3. Develop a predictive model for medical versus surgical management

2.2 A secondary exploratory objective is to determine the usefulness of serial fecal calprotectin levels as a predictive biomarker of NEC. We hypothesize that tracking changes in fecal calprotectin levels from baseline can identify preterm infants with and without NEC.

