## 4.0 Study Endpoints

4.1 The primary endpoint for this study will be feasibility of recruitment into a diagnostic RCT and implementation of BUS intervention in infants with suspected NEC. Feasibility parameters to be assessed include recruitment, randomization, retention, and crossover. Recruitment will be measured as proportion of eligible infants who are enrolled, while randomization will be proportion of enrolled infants who develop NEC suspicion and undergo randomization. Retention will be defined as proportion of infants who complete the study. Crossover will be measured by proportion of infants randomized to standard of care who crossover to BUS arm. Successful implementation of intervention will be assessed by (1) proportion of properly completed BUS studies by sonographers; (2) proportion of adherence to standardized reporting template by radiologists, and (3) timeliness of stool collection in proximity to the BUS. For the secondary endpoint measures, time to achieve full enteral feeds will be defined as days to reach enteral feeds of 120mL/kg/day following suspension of feeds due to suspected NEC; and total antimicrobial days will be defined as days treated with empiric antibiotics due to suspected NEC. For the exploratory aim, the primary endpoint will be changes in serial fecal calprotectin levels and its association with NEC diagnosis.

[figure not shown]

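### Two different stools are called the fecal calprotectin baseline, and the one formally defined (five weeks of age or older, on full feeds) falls after any NEC concern that arises before it is met

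*Combined protocol and SAP*

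**What the plan says.** The combined protocol and SAP uses one word for two samples, both in section 6.1.

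- The opening paragraph has no age or feeding condition: "All enrolled subjects will have a baseline fecal calprotectin level obtained at the time of enrollment or with next stool".
- The paragraph on calprotectin measurement takes the same stool without calling it baseline: "Stool will be collected from a diaper following study enrollment regardless of rate of feeds". It then adds another: "We will do an additional collection of stool after five weeks of life to get a baseline calprotectin level". The formal definition follows: baseline "is defined as an infant who is greater than or equal to five weeks of age and is tolerating full enteral feeds", with a minimum of 120 mL/kg/day.

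That paragraph also schedules three stools after any NEC concern, with no minimum age, and one at resolution, once 120 mL/kg/day or more has been tolerated for at least two days.

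The aim appears in three places. The Study Summary (1.0) says: "Explore the usefulness of serial fecal calprotectin levels as a predictive biomarker for NEC". Section 2.2 hypothesizes that "tracking changes in fecal calprotectin levels from baseline can identify preterm infants with and without NEC". Section 4.1 says that for this aim "the primary endpoint will be changes in serial fecal calprotectin levels and its association with NEC diagnosis". None of the three names a reference stool.

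**The concern.** An analyst computing change from baseline has to choose between two stools that can be weeks apart, and the documents give no rule. Two analysts could both follow the plan and produce different variables, and the choice could be made after the results are seen.

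The formal definition raises a further difficulty. It makes baseline depend on reaching an age and a feeding state, not on coming before the event. An infant with an early NEC concern then gets a reference value only after that concern. A quantity that cannot be known until after the event cannot be part of a predictor of it, and a predictive biomarker is the stated aim.

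**Working it through.** The plan gives no figure on this point to reproduce. Its accrual arithmetic in 20.2 and 20.3 (100 × 0.80 × 0.50 = 40 per year, 80 over two years) is correct and not in dispute. The check is one of timing.

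**Inputs.** Age condition: five weeks = 35 days (6.1). Feeding condition: at least 120 mL/kg/day (6.1). Upper limit of gestation at birth: 32 weeks (11.0), read as 32+0. End of participation: discharge or transfer (6.1, 10.1), or withdrawal (16.0). Days of first NEC concern and the lower gestations are examples chosen here.

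**Earliest formal baseline.** Let T be the first day of life on which both conditions hold, so T ≥ 35. For a first NEC concern on day d before T, the reference follows the concern by T − d. When d < 35 this is at least 35 − d:

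- d = 10: 35 − 10 = at least 25 days
- d = 20: 35 − 20 = at least 15 days
- d = 30: 35 − 30 = at least 5 days

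A concern after day 35, but before full feeds are reached, has the same problem through the feeding condition alone.

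**The event can delay the reference.** Section 4.1 expects feeds to stop for suspected NEC, since it defines a secondary outcome as "days to reach enteral feeds of 120mL/kg/day following suspension of feeds due to suspected NEC". The threshold is the same 120 mL/kg/day. After a suspension, the formal baseline therefore cannot be taken until the infant has reached that feeding outcome.

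**Postmenstrual age at the earliest formal baseline** is gestation at birth plus five weeks:

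- born 24+0: 29+0
- born 28+0: 33+0
- born 32+0: 37+0

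An infant born at 32+0 who is discharged or transferred before 37+0 never has a formal baseline, whether sick or well.

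**Can the two baselines be the same stool?** Only if the infant already meets the definition when the enrollment stool is taken. Section 11.0 excludes infants above 36 corrected weeks at admission. Reading that limit as 36+0 = 252 days, an infant born at 31+0 (217 days) can be at most 252 − 217 = 35 days old at admission, so the stools can just coincide. One born at 32+0 (224 days) can be at most 28 days old, so at admission they cannot.

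**The resolution stool.** It requires 120 mL/kg/day or more for at least two days. In an infant aged 35 days or more it therefore also meets the formal definition of baseline, although it follows an event by design. Nothing in the definition excludes an infant with a previous NEC concern.

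**The case against.** The strongest reply is that no passage commits the analysis to change from the five-week stool. Section 4.1 speaks of serial change and association, which can be read as a trajectory with no single reference. Section 2.2 speaks of identifying infants with and without NEC, which could mean discrimination at the time of suspicion. This stands in part: the harm depends on the reading chosen, and a descriptive association can be computed in retrospect from any two stools. But 2.2 still says change from baseline, and only one formal definition is given. Under the discrimination reading, too, a value not yet collected at suspicion cannot help.

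A second reply is that the sampling is adequate. This stands. A reader might infer that infants with early concerns have no pre-event calprotectin at all. The documents do not support that, because an enrollment stool is planned for every infant. For a repeat concern, the earlier resolution stool also comes before the later event. A pre-event stool is missing only where the first stool after enrollment came after the concern, or was not obtained.

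A third reply is that the age-and-feeding standard was deliberate and that the enrollment stool is no uniform alternative, since age at enrollment varies and no criterion excludes a NEC concern before admission. This also stands. It argues against discarding a five-week stool that truly precedes an event. It does not justify using one that follows it.

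**Conclusion.** The point holds as a fault in the definition of the reference, and it should be corrected before analysis. Two stools share one label, the hypothesis does not choose between them, and the formal definition yields a post-event reference or none for any infant whose concern comes before it is met. Infants who meet the definition before their first NEC concern are not affected.

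The size can be stated only as timing: no formal baseline before day 35, and a gap of at least 35 − d days for a first NEC concern on day d below 35. The documents give no distribution of age at first NEC concern or at full feeds, so neither the number affected nor the direction of any bias can be derived. A formal baseline may be missing because an infant died, or because a well infant went home early.

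A reader might also infer that the trial's main result is compromised. It is not. The feasibility and implementation measures in 4.1 use no change in calprotectin, so only the exploratory calprotectin aim is affected. The conclusion about prediction assumes that 2.2 means what it says, namely change from a reference value.

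**What to change.** Amend 2.2, 4.1 and 6.1 as follows.

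- For each NEC concern, the reference for change must be a stool collected before that concern.
- Name the enrollment stool as the reference for any event that precedes the five-week full-feed stool.
- Give the five-week stool a separate label, such as 'age/feeding reference', and never use it to compute change for an event that precedes it.
- Where both stools precede the event, pre-specify one as the main reference and use the other in a sensitivity analysis. State whether the resolution stool of one NEC episode may serve for a later one.
- Adjust for postnatal age at sampling.
- Report infants with no pre-event stool separately, by NEC outcome.
- If 4.1 means a trajectory without a reference stool, say so and align 2.2 with it.

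The cost is mainly wording and an analysis rule. Both stools are already planned, and the stool label in 7.0 already has a field for day of life. The downside is small: reference stools will differ in age and feeding state, and infants without a pre-event stool leave the change analysis.

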## **7.0 Data and Specimen Banking**

7.1 By consenting to the study, patients will allow the collected stool samples to be stored for future research in [name] laboratory (IBC protocol 18-28).

7.2 The Premature Infant Stool Microbiome Repository will be comprised of stool samples that will prospectively be used to study NEC and/or the microbiome of the bowels in premature infants. The purpose of this database is to provide a CMH-wide bank of specimens that will be used for future research for projects involving the study of NEC and/or bowels of premature infants.

7.3 Repository Director – The Director is responsible for the design, development, implementation, and management of the repository. The Director is the person ultimately responsible for repository's compliance with all applicable federal, state, local laws and CMH institutional policies. The Director is responsible for ensuring: 1) the Repository operates within budget; 2) Informed consent is obtained, documented, and stored in compliance with IRB regulations and institutional policies; 3) Repository personnel are appointed, trained, and supervised by the Director to ensure there is an adequate number of staff with adequate experience and assigned responsibilities commensurate with capabilities; and 4) employ a quality assurance system to ensure the Repository's operation is in compliance with the SOP, IRB approval, regulations, and institutional policies.

7.3.1 Repository Manager – The Repository Manager maintains the operation of the day-to-day activities of the Repository, such as submitting accurate and timely information for continuing review, reporting to the IRB any adverse events, unexpected problems, or protocol deviations/violations, and maintaining repository records appropriately.

7.3.2 Technical staff – Responsible for implementation of policies and procedures established by Director. Duties of each staff member are commensurate with their job description.

7.3.4 Contributing Investigators – Persons who provide data/specimens to the repository for storage.

7.3.5 Recipient Investigators – Persons who query or extract data/specimens from the repository for use in future research projects.

Sample size is approximately 80 donors per year from CMH in accordance with inclusion/exclusion criteria to the NEC and Preemies study. (Section 11.0). Stool will be collected by the bedside ICN RN directly from the diaper into a specimen cup. A small amount of stool will be taken in order to complete the calprotectin testing, the unused stool will be stored in the repository.

Time-Line: Stool samples should be stored at 4 degrees C. For microbiome analysis, stools should be transferred to Eppendorf tubes and stored at -80 degrees C preferably within 24-36 h.

Procedure:

- \* Wash your hands thoroughly before beginning the collection.
- \* Collect pre-weighed Eppendorf tubes from [name] Lab (note weight).
- \* Open the Eppendorf tubes.
- \* Using the wooden stick, collect a small amount of feces from the specimen cup.
- \* Weigh the tube with feces.
- \* Discard the rest of the feces after completing Calprotectin studies in the usual way.
- \* Firmly screw the lid on the specimen container (taking care that it is not cross-threaded).
- \* Please ensure the specimen jar is correctly labelled with your de-identified study code number and samples number (ex., ID-Stool 1, Stool 2), date & time sample was collected. Please record the weight of stool in the tubes.
- \* Place the sealed specimen jar in the plastic hazard bag provided and immediately store -80 0C.

INFANT STOOL SAMPLE LABEL

Participant ID #: -----

Date of collection: \_\_\_\_/\_\_\_\_/\_\_\_\_

Stool sample id:

Day of life stool was collected:

Time Collected: \_\_\_\_:\_\_\_\_ am/pm

Weight of stool:-----

7.3 The stool samples will be labeled with the study ID of the enrolled patient in the NEC and Preemies study. The stool samples will be labeled with a letter in alphabetical order for subsequent stool samples (i.e. 1-a, 1-b, etc.).

7.4 Repository Personnel will view and record PHI for inclusion into the Repository: [Manager, Staff, etc.]. Medical information is protected under federal, state, local privacy laws and under the terms of the consent process. CMH employees with access to the repository may not disclose information in

accordance with the Administrative Policy, Confidentiality. Database is password protected and accessible only by Repository personnel.

7.5 Only projects researching NEC or bowel microbiome in premature infants will be considered for use of the Premature Infant Stool Repository. The recipient investigator must have a protocol approved by an IRB for this purpose or an approved Exemption from the IRB. This documentation must be provided before samples/data are distributed.

Recipient investigators include CMH investigators and non-CMH investigators.

7.6 A written 1-2 page request summarizing the project for which the samples are requested must be submitted to the Repository Director. The request must contain the following details: number of samples, ethnicity of donors, amount and concentration of DNA in addition to a brief project summary (abstract), the specific aims/goals, significance and experimental design and methods (Appendix 5).

Only recipient investigators authorized by the Repository Director will have direct access to the Repository. The Repository will not release any direct identifiers to any recipient investigators (see Form X: Recipient investigator query form).

Information accessed by non-CMH employees may also be bound under non-disclosure or confidentiality agreements. Confidentiality Disclosure Agreement (CDA) will be signed and kept on file for persons not bound by CMH Administrative Policy, [Confidentiality](#) in order to protect the sensitive information that they have access to. See Administrative Policy, [Confidentiality Agreement](#).

Sample:

Data	Repository Personnel	CMH Recipient Investigators	Non-CMH Recipient Investigators
Identifiable data set (Form A)	All/Manager only	Available upon request and IRB approval	Not released
De-identifiable data set (Form B)	All	Available upon request and IRB approval	Available upon request and IRB approval

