## **13.0 Local Number of Subjects**

13.1 This pilot study will enroll 80 NICU patients per year, aiming to randomize 40 patients a year with suspected NEC.

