## 20.0 Data Management and Confidentiality

20.1 This is a pilot study only to evaluate feasibility of a larger clinical trial. We will use the pilot data in the future to perform a power analysis for the larger study.

20.2 We anticipate having to approach ~100 patients/year to achieve the 40 patients/year needed for our pilot study. We are assuming a NEC suspicion incidence rate of 50% and approximately 20% of parents/patients declining to consent for the study (e.g. 100 patients \* 80% consent rate \* 50% with NEC suspicion = 40 patients/year).

20.3 With a target of 80 patients randomized, we anticipate the enrollment period to last ~2 years. We will stop consenting patients as soon as we meet our desired enrollment.

20.4 A certificate of confidentiality will not be sought for this study.

20.5 Study data will be evaluated by the PI throughout the duration of the study for QA.

20.6 Patient information will be maintained in a REDCap application and will be housed within the CMH Data Center by the Division of Biomedical Informatics. The hosting server has an internal failover two-node cluster. The CMH Data Center is constantly staffed by qualified personnel and physical access is limited to authorized personnel. The

Center has optimized conditions for the servers and stabilized electrical supply. The database has a full backup. The database server is located inside the CMH corporate firewall. A person must have CMH system access to login. Additional security for the study patient database restricts access to only those persons specifically granted authorization by the Principle Investigator. It is possible for data to be downloaded from REDCap. Individuals who lack authority to see confidential data can download reports with non-identifiable data only. The core research group will have the ability to download sensitive fields and if such a download occurs, REDCap maintains a record of who, what, when, and to where copies of the database were imported.

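### Stool banking is bundled with trial consent and refusal reasons are not logged, so the primary recruitment proportion may understate acceptability of the RCT by an unknown amount

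*Combined protocol and SAP*

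**What the plan says.** Section 7.1 ties the repository to trial consent: "By consenting to the study, patients will allow the collected stool samples to be stored for future research". Section 7.2 sets an aim for the bank beyond this trial: "The purpose of this database is to provide a CMH-wide bank of specimens that will be used for future research". Later in section 7.0 the bank is sized: "Sample size is approximately 80 donors per year from CMH", under the trial's own eligibility criteria. Section 13.1 gives the matching trial figure: "This pilot study will enroll 80 NICU patients per year, aiming to randomize 40 patients a year with suspected NEC". Planned donors per year therefore equal planned enrolment per year. The consent sections (25.0 and 26.0) describe no separate decision about banking.

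Section 4.1 defines the feasibility measure: "Recruitment will be measured as proportion of eligible infants who are enrolled". Section 20.2 plans on about 100 approaches per year, with "approximately 20% of parents/patients declining to consent for the study", and gives no breakdown of that refusal by reason. Section 14.4 lists four items for the pre-screening log: date of birth, record number, eligibility, and whether the family chose to take part. A reason for declining is not among them.

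On access to the bank, 7.5 admits recipient investigators from inside and outside the hospital, provided they have IRB approval or an exemption. The table after 7.6 makes identifiable data available to the hospital's own investigators on request and with IRB approval, and withholds it from outside investigators. The text of 7.6 says that no recipient investigator receives direct identifiers.

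**The concern.** The bank is a different request from the trial. It serves future projects on NEC or the preterm bowel microbiome, and it may supply outside investigators. Some families could be content with a randomised comparison of imaging and still not want stored samples. Under 7.1 such a family cannot enrol. Its infant stays in the eligible denominator and is missing from the numerator, so any effect on the recruitment proportion runs in one direction only.

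This matters because of what the proportion is for. Sections 2.1 and 20.1 present the pilot as the basis for a larger trial, which 2.1 describes as multi-center. The repository is a single-hospital resource, and nothing says that the larger trial would carry it. The figure that needs to transfer is acceptance of the RCT. The pilot as written yields acceptance of the RCT together with the bank. Without a recorded reason for refusal, the listed data do not allow the two to be separated after accrual.

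**Working it through.** **Inputs.** About 100 approached per year, 20% declining and 50% with NEC suspicion (20.2); 80 enrolled and 40 randomised per year (13.1); "160 subjects enrolled" in total (1.0); 80 randomised in about 2 years (20.3). The share of refusers who object only to the bank, f, is not in the documents and is varied as an assumption.

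**Step 1: the plan's own figures.**
- Enrolled per year: 100 x 0.80 = 80.
- Randomised per year: 80 x 0.50 = 40.
- Over 2 years: 160 enrolled and 80 randomised.

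All agree with the stated figures.

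**Step 2: acceptance of the RCT alone.** The 20% is refusal of the study, and under 7.1 the study includes the bank. Bank-only refusals therefore already lie inside the 20%.

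- Acceptance of the RCT alone = 0.80 + 0.20 x f
- Understatement = 20 x f percentage points
- Randomised per year if banking were optional = 100 x (0.80 + 0.20 x f) x 0.50
- Approaches needed for 160 enrolled = 160 / (0.80 + 0.20 x f), rounded up

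| Assumed f | Acceptance of RCT alone | Understatement (points) | Randomised per year if unbundled | Approaches for 160 enrolled |
|---|---|---|---|---|
| 0 | 80% | 0 | 40 | 200 |
| 10% | 82% | 2 | 41 | 196 |
| 25% | 85% | 5 | 42.5 | 189 |
| 50% | 90% | 10 | 45 | 178 |
| 100% (upper bound) | 100% | 20 | 50 | 160 |

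**Step 3: scale against sampling error.** If 160 of 200 families consent, the Wilson 95% interval is 73.9% to 85.0%. The upper limit is 85.0 - 80.0 = 5.0 points above the estimate, so the bias exceeds sampling error only if f is above roughly 25%.

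**Step 4: the denominator.** The 80% is per family approached, whereas the endpoint counts eligible infants. If only a fraction a of eligible infants is approached, the observed proportion is 0.80 x a and the understatement due to the bank is 20 x f x a points. The table takes a = 1 and so shows the largest value for each f. Eligible infants who are never approached lower the measure for reasons unrelated to banking.

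**The case against.** The strongest reply is that enrolled over eligible is a correct measure of recruitment to this protocol as designed. It misleads only as a forecast for a trial without a bank, and the documents do not say whether the larger trial will have one. That stands, and it limits the point to what can be carried forward.

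The added request is also modest. The bank takes only stool left over after calprotectin testing, and 6.1 already collects serial stools and keeps samples for the length of the study. The proportion of families who would decline for this reason alone could be zero. That stands too.

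Whether banking is truly compulsory cannot be settled from the protocol text. The consent form is not part of the text reviewed, and section 7.3 makes the Repository Director responsible for seeing that informed consent is obtained and documented. An optional choice on the form cannot be excluded. If there is one, however, 7.1 misdescribes it, and a donor figure equal to full enrolment is too high unless every family agrees. Likewise, the log contents in 14.4 need not be exhaustive, but no reason field is stated.

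A reader might infer that bundling cuts accrual. Taking 2, 5 or 10 points off the 80% gives 100 x 0.78 x 0.50 = 39, then 37.5 and 35 randomised per year. At 35 per year, 80 infants take 80 / 35 x 12 = 27.4 months, just past the 27-month accrual stage in 10.2. The documents do not support this. It treats the 80% as acceptance of the RCT without the bank, whereas 20.2 refers to consent to the study, which under 7.1 includes the bank. It also treats 100 approaches per year as a ceiling, when 20.2 gives it as the number needed. Section 28.1 reports over 150 infants per year at or below 28 weeks, and eligibility extends to 32 weeks. Even at 70% consent, 40 / (0.70 x 0.50) = about 114 approaches would suffice, and nothing shows that to be out of reach.

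A reader might also infer that identifiable data pass freely to other investigators. The table requires both a request and IRB approval, and 7.6 rules out release of direct identifiers. Those two statements need reconciling with each other, but they are safeguards.

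**Conclusion.** The point holds as a minor, inexpensive improvement. On the visible text, consent to the trial includes consent to the bank and no reason for refusal is listed for the log. The recruitment proportion may therefore understate acceptability of the RCT by 20 x f percentage points, with f unknown and possibly zero. Values of 2, 5 and 10 points correspond to assumed f of 10%, 25% and 50%; none of these is an estimate.

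The planned 40 randomised per year and the sample size stand, and no accrual delay follows. The conclusion assumes that the consent form mirrors 7.1, that the 20% refusal applies to the whole study including the bank, and that the larger trial would not carry the same bank. It would be too strong to say that the measure does understate acceptability, since no document gives a rate of bank-only refusal.

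**What to change.** 1. Change 7.1 so that banking is a separate yes/no choice on the same form and is not required for enrolment. Stool left over from infants without bank consent is then not banked. If the form already offers this choice, correct 7.1 and the 80-donor figure in 7.0 to match it.
2. Add a reason for refusal to the log in 14.4, for example: randomised trial, ultrasound, stool tests, bank, other, not given.
3. Report RCT recruitment and banking acceptance as separate proportions.
4. In section 7.0, reconcile the table's provision for identifiable data (request plus IRB approval) with the statement in 7.6 that no direct identifiers are released, so that families are told one consistent thing.

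The cost is a tick-box, one log column and an IRB amendment. The downside is possibly fewer than 80 banked donors per year. Calprotectin testing for the trial, imaging, randomisation and sample size are unchanged. The refusal-reason column is worth having even if bank-only refusals prove rare, because a feasibility study should learn why families decline.
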